6.1. Critical Assessments Prior to Investigational Product Administration

The following assessments are required before dosing (i.e., before initiating randomized treatment):

- Electronic fetal monitoring to confirm that the fetal heart rate pattern remains reassuring
- Re-assess that tocolytic therapy is still indicated, according to the investigator's medical discretion.
- Liver function tests from a local laboratory to confirm that ALT is not $\geq 2 \times$ ULN OR bilirubin is not $> 1.5 \times$ ULN ($> 35\%$ direct bilirubin), if available (see Section 6.3.1). An isolated bilirubin $> 1.5 \times$ ULN is acceptable if bilirubin is fractionated and direct bilirubin is $< 35\%$. Dosing may be started prior to the availability of these results.
- Electrocardiogram that is interpreted by the investigator to not have any significant abnormalities that may place the subject at risk for a cardiopulmonary complication during the study

If the fetal heart rate pattern is nonreassuring, tocolytic therapy is no longer indicated, levels of ALT or bilirubin are abnormal (if results are available), or the ECG has been interpreted to have clinically significant abnormalities, the subject cannot be dosed and will be withdrawn from the study (see Section 4.4.1).

6.2. Efficacy

Collection of efficacy endpoint data requires a thorough review of the hospital medical records. Review of the maternal hospital record is the responsibility of the investigator obstetrician and review of the newborn hospital record is the responsibility of the subinvestigator neonatologist.

6.2.1. Time to Delivery

The time to delivery will be assessed from the start of study treatment administration (time 0) in the Inpatient Randomized Treatment Phase until delivery. For this efficacy assessment, medical records for the delivery and hospitalization for mother and newborn will be reviewed in order to record the following information:

- Date and time of delivery
- Mode of delivery
- Indication for delivery

Operational procedures will be instituted to optimize data collection and reporting consistency in those situations where the subject's delivery is performed by her referring primary care obstetrician. Details of these procedures are provided in the SPM.

6.2.2. Neonatal Composite and Other Outcomes

The proportion of neonates with any diagnosis from the neonatal morbidity and mortality composite will be determined from time of delivery up to 28 days after the EDD of $40^{0/7}$ weeks. For infants who are still hospitalized 28 days post EDD, no further data will be collected as part of this study. Data after 28 days post EDD may be captured as part of a separate infant follow-up study.

For this efficacy assessment, newborn medical records will be reviewed in order to record the following information:

- Variables relevant to the composite (see complete list in Section 6.2.4)
- Hospital length of stay
- Neonatal admission to a specialized care unit and length of stay
- Newborn hospital readmission and length of stay
- Ambulatory surgery

6.2.3. Primary Efficacy Endpoint

The primary efficacy endpoint is time to delivery from the start of IP administration until delivery, based on a records review.

6.2.4. Key Secondary Efficacy Endpoints

- Proportion of births prior to $37^{0/7}$ weeks' gestation – ascertain the GA at delivery based on a records review
 - Proportion of births at term ($37^{0/7}$ to $41^{6/7}$ weeks' gestation) – ascertain the GA at delivery based on a records review
 - Length of neonatal hospital stay – confirm duration (in days) of neonatal hospital admission from the medical records
 - Proportion of neonates with any diagnosis from the neonatal morbidity and mortality composite determined up to 28 days after EDD (of $40^{0/7}$ weeks) – proportion of infants with any one of the following:
 - Fetal or neonatal death
 - RDS
 - Requiring continuous positive airway pressure or mechanical ventilation. Diagnosis requires a chest radiograph consistent with RDS (reticulogranular appearance to the lung fields or air bronchograms) within the first 24 hours of life
- OR
- Received surfactant for a clinical picture of RDS within the first 24 hours of life

- Bronchopulmonary dysplasia at ≥ 36 weeks postmenstrual age (determined by adding chronological age to GA at delivery), defined as follows:
 - >21% supplemental oxygen requirement
 - OR
 - Use of high-flow nasal cannula at ≥ 1 L (21% oxygen)
- Necrotizing enterocolitis or isolated perforation
 - Diagnosed by radiographic evidence of Stage II or higher according to Bell's staging criteria (fixed/unchanging bowel loops, pneumatosis intestinalis, portal venous gas, pneumoperitoneum)
 - OR
 - Pneumatosis intestinalis, bowel necrosis, or perforation noted at surgery
- Sepsis based on positive blood culture with clinical features of sepsis
- Meningitis based on positive cerebrospinal fluid culture performed as part of infection workup
- Retinopathy of prematurity
 - Confirmed by an ophthalmologist based on international committee Stage 4 or 5
 - OR
 - Requiring surgical treatment with laser or other surgical intervention including cryotherapy or treatment with anti-VEGF (vascular endothelial growth factor)
- IVH
 - Grade 3 or 4 (severe IVH)
 - OR
 - Any grade of IVH with posthemorrhagic hydrocephalus requiring a shunt
- White matter injury, documented on cranial ultrasound or magnetic resonance imaging, as indicated by the following:
 - Multiple cystic lucencies in periventricular white matter (may be bilateral or unilateral, may vary in size, and be diffuse or focal in distribution)
 - OR
 - Porencephalic cyst (not including subependymal or choroid plexus cysts)
 - OR
 - Persistent ventriculomegaly, moderate to severe
- Cerebellar hemorrhage (unilateral or bilateral)

- Retosiban clearance and volume of distribution and the effect of covariates on these parameters

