Estimated date of delivery	Defined as 40 ^{0/7} weeks' gestation for all subjects
Gestational age	Determined by (1) known fertilization date, either in vitro fertilization or intrauterine insemination or (2) a best estimated due date confirmed or established by the earliest ultrasound performed prior to 24 ^{0/7} weeks' gestation
Postmenstrual age	Determined by adding chronological age to gestational age at delivery

Trademark Information

Trademarks of the GlaxoSmithKline group of companies	Trademarks not owned by the GlaxoSmithKline group of companies
NONE	MedDRA Tractocile

PROTOCOL SUMMARY

Rationale

Mortality and morbidity in premature infants are inversely proportional to gestational age (GA) at birth; babies born before $32^{0/7}$ weeks' gestation have the greatest risk for death and poor health outcomes [Saigal, 2008]. The inverse relationship between neonatal mortality and morbidity and GA at birth has been the basis for treatments to prolong pregnancy with the goal of improving neonatal outcomes by allowing continued maturation of fetal organ systems. Tocolytic therapy is recommended for short-term delay of delivery in order to administer antenatal corticosteroids, but there is no evidence that current tocolytic regimens improve neonatal or infant outcomes beyond the effect of antenatal corticosteroids [Sanchez-Ramos, 1999; RCOG, 2011; ACOG, 2012; Roos, 2013]. Unfortunately, neonatal mortality and morbidity remain disproportionately high for this study population despite antenatal corticosteroids and highlight a critical need for new therapies to prolong pregnancy and improve neonatal outcomes.

Results from the OTA105256 Phase II found that retosiban prolonged pregnancy and reduced prematurity rates in women between $30^{0/7}$ and $35^{6/7}$ weeks' gestation. Retosiban, given intravenously over 48 hours, increased days to delivery by a mean of 8.2 days relative to placebo, and this difference was consistent across GAs. The emerging safety profile for retosiban also appears favorable. All reported adverse events (AEs) (maternal, fetal, and neonatal) were generally consistent with either those reported in the investigator's brochure (IB) or in the population under study. A summary of the complete results for Study OTA105256 is included in the IB [GlaxoSmithKline Document Number CM2006/00201/05].

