1.2. Rationale

This study is being conducted based on the results of the OTA10256 study that demonstrated significantly longer time to delivery. Specifically, OTA105256 was a Phase II study of retosiban for the treatment of spontaneous preterm labor in women with singleton pregnancies and intact membranes. This study initially examined the pharmacokinetics, dose response, and safety of retosiban in women for whom the gestational age (GA) was restricted to $34^{0/7}$ and $35^{6/7}$ weeks. Retosiban was given intravenously with the loading dose and infusion rate increased in a stepwise fashion every 3 hours to achieve target plasma concentrations. Alternate tocolytic drugs were not permitted during the study's IV infusion phase. Twenty-nine adult subjects (ages 18 to 37 years) were enrolled into Parts A and B. An interim analysis, indicating retosiban suppressed contractions and prolonged pregnancy, resulted in an additional cohort (Part C with a lowered GA to $30^{0/7}$ weeks) to evaluate retosiban in a clinical population and setting more consistent with current practice guidelines for tocolytic use. Sixty-four adult subjects (ages 18 to 41 years) were enrolled, randomly assigned to treatment, and dosed in Part C.

Data from Study OTA105256 found that retosiban treatment, at a dosing regimen of 6-mg load over 5 minutes, then 6 to 12 mg/hour based on response, was associated with a higher proportion of females achieving uterine quiescence and a significant difference in time to delivery and reduction in preterm births. Uterine quiescence was defined as 4 or fewer contractions per hour with no change in cervical dilation greater than 1 cm. Using partial informative priors, which partially weighted the Part A/B response rates for retosiban and placebo, the posterior mean response rate within the initial 6 hours of treatment was 62% in the retosiban group compared with 41% in the placebo group. The posterior relative risk of achieving quiescence was 1.53 (95% confidence interval [CI]: 0.98, 2.48).

Retosiban treatment was also associated with a significant difference in time to delivery and births prior to 37 weeks of gestation. The posterior mean difference in time to delivery was 8.2 days relative to placebo (95% CI: 2.7, 13.74). The percent of preterm births in the retosiban and placebo groups was 18.7% and 47.2%, respectively. The posterior relative risk for preterm birth in the retosiban group was 0.38 (95% CI: 0.15, 0.81).

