4. ANALYSIS POPULATIONS

Population	Definition / Criteria	Analyses Evaluated
All Randomized	
 • Consists of all mothers randomly assigned to treatment regardless of whether they actually are treated. • Subjects will be presented by their planned randomized treatment 	
 • Subject Disposition
Randomized but not dosed	
 • Consists of all mothers that are randomized but fail to receive any study treatment. • Subjects will be presented by their planned randomized treatment. 	
 • Subject Disposition
Maternal Safety	
 • Mothers randomly assigned to treatment who have been exposed to study treatment. • Randomly assigned subjects will only be excluded if there is clear evidence the subject did not receive IP. • Subjects will be analyzed according to their actual treatment. Any subject who received both treatments (retosiban and atosiban) will be assigned to retosiban group for actual treatment. 	
 • Maternal and fetal safety
Neonatal Safety	
 • Consists of neonates whose mothers received randomized treatment. • Subjects are analyzed according to the actual treatment their mothers received. • Any subject who received both treatments (retosiban and atosiban) will be assigned to retosiban group for actual treatment. 	
 • Neonatal safety
Maternal ITT	
 • Consists of all mothers randomly assigned to treatment who have been exposed to study treatment irrespective of their compliance to the planned course of treatment. • Subjects who are randomly assigned but fail to receive any study treatment will be presented separately. 	
 • Maternal and fetal efficacy endpoints
Neonatal ITT	
 • Dataset comprises all neonates whose mothers are the randomized Subjects who have been exposed to study drug, i.e., mothers from the ITT Population. 	
 • Neonatal efficacy endpoints

NOTE :

- Please refer to Section 11.11 Appendix 11: List of Data Displays which details the population to be used for each display being generated.

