11.5.4. Efficacy

Calculation of Time to Delivery

- Once delivery is confirmed, the maternal delivery and hospitalization records will be reviewed for data collection by the investigator obstetrician. The time to delivery is calculated as the days between the delivery and start time of the infusion of IP using the formula below:

$$\text{Time to delivery (days)} = (\text{date/time of delivery} - \text{date/time of start of infusion}) / (24*60)$$
The exact date/time of delivery and infusion will be used to determine the time to delivery.
- Time to delivery or retreatment/subsequent preterm labor is defined as the days between start time of the infusion of IP and the first occurrence among delivery, retreatment and subsequent preterm labor in a similar fashion to the time to delivery.

Calculation of Neonatal Composite Endpoint

Neonatal Composite Endpoint

The presence of any of the following endpoints determined from review of medical records will lead to a value of 1 for the neonatal composite endpoint and 0 otherwise:

- Fetal or neonatal death
- Respiratory Distress Syndrome (RDS)
 - Requiring continuous positive airway pressure or mechanical ventilation. Diagnosis requires a chest radiograph consistent with RDS (reticulogranular appearance to the lung fields or air bronchograms) within the first 24 hours of life

OR

- Received surfactant for a clinical picture of RDS within the first 24 hours of life
- Bronchopulmonary dysplasia at ≥ 36 weeks postmenstrual age (determined by adding chronological age to GA at delivery), defined as follows:
 - >21% supplemental oxygen requirement

OR

- Use of high flow nasal cannula at ≥ 1 L (21% oxygen)
- Necrotizing enterocolitis or isolated perforation
 - Diagnosed by radiographic evidence of Stage II or higher according to Bell's staging criteria (fixed/unchanging bowel loops, pneumatosis intestinalis, portal venous gas, pneumoperitoneum)

OR

- Pneumatosis intestinalis, bowel necrosis, or perforation noted at surgery
- Sepsis based on positive blood culture with clinical features of sepsis
- Meningitis based on positive cerebrospinal fluid culture performed as part of infection workup
- Retinopathy of prematurity
 - Confirmed by an ophthalmologist based on international committee Stage 4 or 5

OR

- Requiring surgical treatment with laser or other surgical intervention including cryotherapy or treatment with anti-VEGF (vascular endothelial growth factor)
- Intraventricular Hemorrhage (IVH)

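### The bronchopulmonary dysplasia component has no limit on gestational age at birth and no minimum duration, so an infant born at 36 0/7 weeks or later can meet it on day 1 through transient respiratory support.

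*Protocol*

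**What the plan says.** Protocol 6.2.4 places BPD at or above "36 weeks postmenstrual age (determined by adding chronological age to GA at delivery), defined as follows". Either of two findings then suffices: a greater-than "21% supplemental oxygen requirement", or "Use of high-flow nasal cannula at" 1 L or more. The Definitions table in the protocol gives the same arithmetic for postmenstrual age (PMA): "Determined by adding chronological age to gestational age at delivery".

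Protocol 6.2.2 sets the observation window: the composite "will be determined from time of delivery up to 28 days after the EDD". SAP 11.5.4 repeats the BPD wording and gives the scoring rule: "The presence of any of the following endpoints determined from review of medical records will lead to a value of 1". The SAP Section 4 entry for the Neonatal ITT population reads: "Dataset comprises all neonates whose mothers are the randomized Subjects who have been exposed to study drug".

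None of these places states a maximum GA at birth, a minimum postnatal age or a minimum duration of support. Protocol 6.3.7.2 does restrict events to infants born before 37 completed weeks. That restriction governs only the reporting of disease-related events, and BPD is not on that list.

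**The concern.** PMA starts at GA at birth. For an infant born very early, reaching 36 weeks PMA takes weeks or months, so support at that point reflects a persisting lung problem. For an infant born at 36 0/7 weeks or later the time condition is already met at delivery, and the same words then capture support needed for hours on day 1. The component therefore measures different things in early and late births.

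BPD feeds a key secondary endpoint (the composite) and two other secondary endpoints: the composite excluding RDS and the individual component. The SAP adds a version excluding both RDS and mortality. Births at 36 weeks or later are the group that a pregnancy-prolonging drug would enlarge, so misclassification there need not be balanced between arms.

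**Working it through.** **No figure to reproduce.** The documents give no event rate, power or sample size for BPD or for the composite. The check is of the definition, followed by an illustration of size.

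**Step 1: when the criterion can first be met.** Days after birth = max(0, (36 − GA at birth in weeks) × 7).

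| GA at birth (weeks) | Days until 36 weeks PMA |
|---|---|
| 24 | 84 |
| 28 | 56 |
| 30 | 42 |
| 32 | 28 |
| 34 | 14 |
| 35 | 7 |
| 36 or later | 0 |

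**Step 2: whether another rule closes the gap.** The window opens at delivery, all births to treated mothers are included, and any listed criterion sets the composite to 1. The logistic models in Protocol 8.3.5.1.2 and SAP 8.1.2 adjust for GA at randomization. They do not adjust for GA at birth, so they do not remove the effect.

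**Step 3: interaction with RDS.** RDS requires either airway pressure support or ventilation with a consistent radiograph in the first 24 hours, or surfactant in that period. An infant born at 36 weeks or later with a brief oxygen need can fail RDS and still meet BPD. An infant of that GA who has RDS and a qualifying oxygen or cannula need leaves the composite when RDS is excluded, then re-enters it as BPD.

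**Step 4: illustrative size.** Inputs:
- Share of late births, s. The only figure by arm is from Phase II (Protocol 1.2): "The percent of preterm births in the retosiban and placebo groups was 18.7% and 47.2%, respectively". The complements are 100 − 18.7 = 81.3% and 100 − 47.2 = 52.8% at 37 weeks or later. They stand in for shares at 36 weeks or later, from a study with a placebo control and a different GA range.
- Share of late-born infants with qualifying support, q: assumed 1% to 10%.
- n = 150 per arm with birth data (Protocol 8.2.1).

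False events per arm = n × s × q. Excess = (0.813 − 0.528) × q = 0.285 × q.

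| q | Retosiban | Control | Excess (points) |
|---|---|---|---|
| 1% | 1.2 | 0.8 | 0.3 |
| 2% | 2.4 | 1.6 | 0.6 |
| 5% | 6.1 | 4.0 | 1.4 |
| 10% | 12.2 | 7.9 | 2.9 |

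With equal shares of late births the excess is 0 at every q. At the 97 women actually randomized, about 48 per arm, the excess is 48 × 0.285 × 0.01 = 0.1 to 48 × 0.285 × 0.10 = 1.4 infants.

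**Step 5: effect on the full composite.** Assume a 30% true event rate in earlier births and none in later births. With no false events the rates are 0.187 × 0.30 = 5.6% and 0.472 × 0.30 = 14.2%, odds ratio 0.36. At q = 5% they become 5.6 + 4.1 = 9.7% and 14.2 + 2.6 = 16.8%, odds ratio 0.53. This treats every false BPD event as new. In practice some of these infants would already count through RDS, so it overstates the effect.

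**The case against.** The best counter-argument is that the criteria qualify a reported diagnosis and do not create one. The endpoint is worded as neonates with any diagnosis from the list, and a neonatologist reviews the records. SAP 11.5.4 also defines a modified composite that adds all reported neonatal events, such as RDS without recorded ventilation or surfactant. That suggests the main composite needs a reported event plus supporting criteria. On that reading a neonatologist would rarely label a term infant with a day of oxygen as BPD, and a wrong entry would be visible in the listing of composite components. This makes the number of false events uncertain. It does not close the gap: the oxygen or cannula rule is the only operational definition given, and SAP 11.5.4 scores 1 when any criterion is present.

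Four stronger readings are tempting and are not supported:
- **That only infants born at 36 weeks or later are affected.** An infant born at 35 weeks and supported on day 7, or born at 30 weeks and given oxygen on readmission at 38 weeks PMA, also meets the words. Such cases fall on earlier births and would offset part of any arm difference.
- **That the composite is biased against retosiban as a matter of course.** This requires more late births on retosiban. With equal shares there is no expected arm difference, so the gap does not by itself inflate the type I error.
- **That transient oxygen use dominates the component.** The documents give no rate of support and none of true BPD.
- **That about 45% of atosiban births occur at 36 weeks or later.** Protocol 8.2.1 assumes 55% deliver within 3 weeks of randomization, which is a different quantity. A woman entering at 24 weeks and delivering 5 weeks later has a 29-week birth.

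The practical stakes are also limited: SAP 8.1.2 lists the composite last in its testing order, and the trial stopped at 97 women.

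**Conclusion.** The concern holds as a defect of definition. As written in both documents, an infant born at 36 0/7 weeks or later with any qualifying oxygen need or cannula use meets BPD from day 1. The consequence is most direct for the individual component and the composite excluding RDS.

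The arm effect is conditional. If retosiban shifts births past 36 weeks and support rates among late-born infants are similar between arms, the expected bias runs against retosiban. The range of 0.3 to 2.9 percentage points is illustrative: it rests on an assumed 1% to 10% support rate and on borrowed Phase II birth shares. The effect on the full composite is smaller because of overlap with RDS.

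**What to change.** In Protocol 6.2.4 and SAP 11.5.4, count BPD only in infants born before 36 0/7 weeks who meet the oxygen or cannula criterion at 36 weeks PMA or later. Score infants born at 36 0/7 weeks or later as 0 on this component. Show the as-written definition as a sensitivity analysis. Make the change before database freeze, when SAP Section 1 requires decisions on the final analyses to be settled.

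The cost is one programming condition on GA at birth, which SAP 11.5.4 says is captured in the eCRF. There are two downsides. A rare true chronic case in an infant born at 36 weeks or later is not counted in this component. Brief support after 36 weeks PMA would still count in infants born just before 36 weeks or readmitted later, because the change adds no duration requirement.

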6.2.5. Other Secondary Efficacy Endpoints

- Proportion of neonates with any of the composite neonatal morbidity and mortality excluding RDS
- Proportion of neonates with each individual component of the composite neonatal morbidity and mortality endpoints listed in Section [6.2.4](#)
- Neonatal admission to a specialized care unit and length of stay – confirm admission to neonatal intensive or specialized care unit from the medical records
- Newborn hospital readmission and length of stay – confirm any neonatal hospital readmission following the birth hospitalization, the reason for admission, and the length of stay from the medical records
- Ambulatory surgery – confirm any neonatal ambulatory surgery and the indication for surgery from the medical records
- Proportion of births prior to $28^{0/7}$ weeks' gestation
- Proportion of births prior to $32^{0/7}$ weeks' gestation
- Proportion of births ≤ 7 days
- Proportion of births ≤ 48 hours
- Proportion of births ≤ 24 hours

